6.4.3. Study HRQoL Tool

Once consent is given, study personnel will provide a brief demographic questionnaire to the parent or guardian which will also ask them to score their child's HRQoL at the time of consent as well as retrospectively score their child's HRQoL prior to becoming illand if they are already recovering their HRQoL on the worst day of the illness. Parents will be given a brief demonstration and instructions of our diary system and asked to complete this daily (or alternate days) whilst in hospital (or receiving outpatient parenteral antibiotics / OPAT as part of hospital level care at home), weekly once discharged from hospital for one month and then monthly until their child's symptoms have completely resolved with a final contact again at six months. (figure 1) The diary will consist of illness severity questions and HRQoL questionnaires for the child and their parents taking less than 5 minutes to complete. Children over the age of 7 years will be able to fill out their own quality of life questionnaires themselves.

Parents will be offered reminder contact for the diary entries by phone / SMS / email, with the option of completing questions over the phone or internet.

We anticipate that for the families of children with severe disease as a result of varicella, engagement with the study aims will be high and with good communication and weekly reminders there should be limited dropout.

QoL-PoX-H (IRAS 240389)

Figure 1: Timing of diary entries.(*INPATIENT includes receiving outpatient parenteral antibiotics / OPAT as part of hospital level care at home)

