2. SYNOPSIS

Study Title	Quality of Life Effects of Chickenpox on Hospitalised Children and their Families.				
Internal ref. no.	QoL-PoX - hospital				
Study Design	Observational Cohort Study				
Study Participants	Children aged 0-16 years and their carers				
Planned Sample Size	100 (but to allow possible over recruitment to 200)				
Follow-up duration	Up to 6 months after hospital discharge.				
Planned Study Period	1st March-2018 1st Nov 2020 (30m recruitment+6m follow up)				
Primary Objectives	To assess the impact of varicella disease on quality of life,				
Secondary	To assess the impact of varicella disease on healthcare use, financial and health				
Objectives	impact on family unit				
Primary Outcome	- QALY loss of patients and carers				
Measures					
Secondary Endpoints	- Wider financial and health impact on family members of affected patients				
Intervention (s)	none				

3. Relevant Study Documents

- Protocol (this document)
- Consent form
- Parent Information Sheet
- Child Information Sheet
- Daily Diary Inpatient (parental proxy + young person version)
- Weekly Diary for home (parental proxy + young person version)

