4.1.2. Impact on Health Related Quality of Life

The only study quantifying the health related quality of life (HRQoL) lost due to varicella in UK children used a convenience sample of forty two children attending primary care for other reasons whose mothers were asked to recall their child's quality of life at the time they had had chickenpox.[9] This suggested that the QALY loss due to VZV was 4 per 1000 patient cases. However the impact on carer HRQoL or social costs such as time from work / healthcare were not assessed. A similar retrospective method was used in Belgium finding a QALY loss of 4 per 1000 for children not seeking medical care but 10 per 1000 for those who had been ill enough to visit their General Practitioner.[10]

The HRQoL loss of patients hospitalised with VZV has not been assessed in the UK. In our study we will also be assessing carer HRQoL which although recommended by NICE to be included in economic analyses[11] is often overlooked and in previous studies we have found to be a significant additional burden of disease.[12] Of particular interest in children hospitalised with VZV is the persistence of long term sequelae. At discharge QoL-POX-H (IRAS 240389)

Protocol Version 1.5 (27/11/201)

from hospital children are unlikely to be back to a normal health state so we plan to follow them with additional diaries weekly for one month then a final follow up at six months.

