8.2. Methods

Quality adjusted life year loss for children and their parents will be calculated as the reduction in HRQoL from baseline (as reported retrospectively prior to illness) for the time period between development of clinical signs and return to what the parents assess is normal health for their child. A sensitivity analysis will be carried out using baseline "healthy" cohort being assessed in a separate study.

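### Monthly diaries stop at symptom resolution but the QALY window runs to parent-assessed normal health, so a symptom-free child not yet back to normal can go unscored for up to five months

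*Protocol*

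**What the plan says.** The primary outcome in the Protocol synopsis is "QALY loss of patients and carers", with follow-up described as "Up to 6 months after hospital discharge".

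Three places bear on when quality of life is scored after discharge and when the loss stops being counted:

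- **Section 6.4.3 (Study HRQoL Tool)** sets the procedure: diaries weekly for the first month after discharge, then monthly until the child's "symptoms have completely resolved with a final contact again at six months". The same diary carries illness severity questions and the quality-of-life questionnaires for both child and parents.
- **Section 8.2 (Methods)** defines the loss, for children and parents alike, as the reduction from baseline "for the time period between development of clinical signs and return to what the parents assess is normal health for their child".
- **Section 4.1.2 (Impact on Health Related Quality of Life)** summarises the follow-up as "additional diaries weekly for one month then a final follow up at six months" and names lasting sequelae as a particular interest.

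The document list in section 3 has a daily inpatient diary and a weekly home diary, and no separate monthly one.

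**The concern.** The diaries and the QALY calculation end on different events. Section 6.4.3 stops on symptoms; section 8.2 stops on the parents' judgement of overall health. The protocol itself treats these as separate quantities: symptom severity has its own tool and is a secondary outcome (6.2.2), while quality of life is the primary one (6.2.1). A child can be free of symptoms and still below the pre-illness score. For that child the diary has stopped and the QALY window is open.

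Because one diary serves child and parents, the carer part of the primary outcome stops at the same moment.

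This is a matter of data collection. An analysis plan can choose how to bridge a gap, but it cannot recover scores that were never requested. Section 6.4.3 also calls the six-month point only a contact and does not say that quality of life is scored there, so the far end of the gap may have no score either.

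A second, smaller matter is that the rationale omits the monthly diaries that section 6.4.3 contains. In a multisite study the written schedule should read the same throughout.

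**Working it through.** The protocol states no figure on this point that could be reproduced. The check sets the two rules side by side and then measures the possible gap.

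**Step 1: who is affected.** After month 1 there are four combinations:

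| Symptoms (6.4.3 trigger) | Parent's view of health (8.2 trigger) | Monthly diary | QALY window | Scores missing? |
|---|---|---|---|---|
| Continuing | Not yet normal | Continues | Open | No |
| Continuing | Normal | Continues | Closed | No (surplus scores) |
| Resolved | Normal | Stopped | Closed | No |
| Resolved | Not yet normal | Stopped | Open | **Yes** |

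Only the last row is exposed.

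**Step 2: how long the gap can be.** Weekly diaries run to month 1 for everyone, and the next fixed point is month 6. If the last diary is at month m, the interval without scores is 6 − m months. Its maximum, when symptoms resolve by month 1, is 6 − 1 = 5 months. Later resolution shortens it: 3 months if the last diary is at month 3, and 1 month if it is at month 5.

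**Step 3: what could fall in the gap.** The protocol gives no utility deficit for such children, so the deficit d is an assumption, shown over a range. If d is held for the whole interval, the loss is d × (6 − m)/12.

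| Assumed deficit d | m = 1: d × 5/12 | m = 3: d × 3/12 | m = 5: d × 1/12 |
|---|---|---|---|
| 0.02 | 0.0083 | 0.0050 | 0.0017 |
| 0.06 | 0.0250 | 0.0150 | 0.0050 |
| 0.10 | 0.0417 | 0.0250 | 0.0083 |
| 0.20 | 0.0833 | 0.0500 | 0.0167 |

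These are QALYs per affected child. Straight-line recovery over the interval halves each figure; recovery just after the last diary makes it close to zero. Without scores in the interval these courses cannot be told apart, unless the date of return to normal is obtained in some other way.

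**Step 4: after the change.** With monthly diaries continued to the 8.2 end event or month 6, the longest interval without a planned score is one month. The figures in the m = 1 column fall to those in the m = 5 column: from 0.008–0.083 to 0.002–0.017 over the same range of d.

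**The case against.** The strongest reply is that section 6.4.3 is the operative text and asks for complete resolution of symptoms. On an ordinary reading, a child with a residual deficit after stroke or encephalitis still has symptoms and keeps monthly diaries. This stands, and it confines the point to the last row of the table in Step 1.

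Four stronger readings are tempting, and the documents do not support them:

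- *That every child lacks scores between months 1 and 6.* This takes the one-clause summary in the rationale as the schedule. It sits in background text, and a site would most likely follow section 6.4.3.
- *That follow-up thins out in the very children with sequelae.* Section 6.4.3 does the reverse for those whose symptoms persist.
- *That a bias in the cohort mean can be stated.* It would need the share of children affected, their deficit and the direction of error, and the protocol gives none of these. An overestimate also presumes that the date of return to normal is unknown; if it is obtained, section 8.2 closes the window there. The losses of 4 and 10 per 1000 quoted in the rationale are means that do not come from hospitalised children, so they are a poor yardstick for one affected child here.
- *That Figure 1 is wrong.* It is not shown and may already include the monthly entries.

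The missing monthly form in section 3 carries little weight, since the weekly form could be reused. The rule for bridging missing scores belongs in an analysis plan, and its absence is not held against the protocol. None of this reconciles the two end events.

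**Conclusion.** The point holds in a limited form. The mismatch between sections 6.4.3 and 8.2 is plain in the current text, and it touches the primary outcome for children and carers. It matters only for children judged symptom-free before they are judged back to normal. For them the gap is at most five months, and shorter if symptoms last beyond month 1.

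Its effect on the study result cannot be derived from the documents. The figure of 0.008 to 0.083 QALY per affected child is an illustration. It rests on an assumed deficit of 0.02 to 0.20, held for the full five months. The number of such children is unknown and probably small.

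The difference between the rationale and section 6.4.3 is a wording inconsistency. The change is still worth making, because scores that are not collected cannot be restored later and the correction is cheap.

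**What to change.** - **Section 6.4.3:** replace the symptom-based stop with the end event of section 8.2. Monthly child and carer quality-of-life diaries continue after month 1 until the parent states that the child is back to normal health, or until month 6.
- **Section 6.4.3:** state that child and carer quality of life is scored at the six-month contact for all families.
- **Section 4.1.2 (quality of life):** add the monthly diaries to the summary of follow-up.
- **Figure 1:** check that it matches, and change it only if it does not.

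The cost is a wording amendment plus at most four further diaries (months 2, 3, 4 and 5) for families in the exposed group. At under five minutes each, that is under 4 × 5 = 20 minutes per family, using the reminders already planned. The only downside is this small extra burden.

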8. ANALYSIS AND STATISTICAL CONSIDERATIONS

8.1. Methods & Sample size calculation

8.1.1. Primary objectives

We aim to recruit at least 100 families of children with chickenpox in hospital into the HRQoL surveillance arm but would ideally like to recruit 200. This will allow us to adequately quantify the differences in quality of life between ill and healthy states for different secondary complications and different ages. The previous historical recall studies[9],[10] do not describe the distribution of their HRQoL in enough detail to use in a power calculation.[24] Using the EQ5D reference healthy data[25] would suggest a sample size of 100 children would give 90% power to detect a 6% difference in quality of life (p=0.05). However as we would like to perform subgroup analysis for different types of secondary complication this will depend on the number in each group — with a minimum of 25. (personal communication [name] Public Health England), ideally a sample size of 200 will increase the likelihood of capturing enough of each complication type to be able to analyse them separately.

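### For children over 7 who self-complete, QALY loss may subtract the child's own diary scores from a baseline scored only by the parent

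*Protocol*

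**What the plan says.** **Baseline.** Under section 6.4.3, "study personnel will provide a brief demographic questionnaire to the parent or guardian which will also ask them to score their child's HRQoL" at consent. The same form asks the parent to "retrospectively score their child's HRQoL prior to becoming" ill and, if the child is already recovering, to score the worst day. No score given by the child is described at enrolment.

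**Follow-up.** The same section then states: "Children over the age of 7 years will be able to fill out their own quality of life questionnaires themselves". Section 3 (Relevant Study Documents) lists two versions of each diary: "Daily Diary Inpatient (parental proxy + young person version" and "Weekly Diary for home (parental proxy + young person version".

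**Primary calculation.** Section 8.2 says that QALY loss "will be calculated as the reduction in HRQoL from baseline (as reported retrospectively prior to illness", taken over the time from first clinical signs until the parents judge the child to be back to normal. It does not say whose follow-up scores are used.

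**Use by age.** Section 8.1.1 says the sample should allow differences between ill and healthy states to be quantified "for different secondary complications and different ages".

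**The concern.** A QALY loss computed as "the reduction in HRQoL from baseline" is a within-child difference. A rater's habit of scoring high or low cancels only if the same rater supplies both ends. As written, a self-completing child can have a parent's score at one end and the child's own at the other. The gap between the two raters is then counted as health lost or gained for as long as the child is the rater.

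Children up to 7 are rated by the parent throughout, while those above 7 may be a mixture. Results for older children therefore carry a component that results for younger children do not.

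This is a matter of data collection as well as analysis. If the child never gives a pre-illness score, or the proxy diary lapses once the child takes over, no later analysis plan can rebuild a same-rater difference.

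**Working it through.** The protocol gives no figure for parent-child scoring differences, so there is none to reproduce. The check consists of the algebra and a range under stated assumptions.

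**Step 1: where the offset enters.** Let P and C be the parent's and the child's scores of the same health state, with subscript 0 for pre-illness and t for a diary day. The mixed difference can be written in two ways:

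- P0 − Ct = (P0 − Pt) + (Pt − Ct), the parent-rated loss plus the rater gap when ill;
- P0 − Ct = (C0 − Ct) + (P0 − C0), the child-rated loss plus the rater gap when well.

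If the gap b = P − C is the same in both states, the mixed loss is the same-rater loss plus b. Over T days the QALY shift is b × T/365. A positive b overstates the loss and a negative b understates it. With one rater at both ends, b cancels, provided that it is the same in well and ill states.

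**Step 2: shift per self-reporting child.** The offset b and the duration T are both assumed. Twenty-eight days roughly matches the month of weekly diaries after discharge.

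| b | 7 days | 14 days | 28 days |
|---|---|---|---|
| 0.02 | 0.02 × 7/365 = 0.0004 | 0.02 × 14/365 = 0.0008 | 0.02 × 28/365 = 0.0015 |
| 0.05 | 0.05 × 7/365 = 0.0010 | 0.05 × 14/365 = 0.0019 | 0.05 × 28/365 = 0.0038 |

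If the child self-rates on only some days, only those days count towards T.

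**Step 3: shift in the cohort mean.** Section 4.1.1 (Epidemiology and burden of disease) says nearly every child is infected before the age of five, so children over 7 are probably a minority. No share is given. Assume that 5% to 30% of all enrolled children self-rate:

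- low end: 0.02 × 28/365 × 0.05 = 0.00008, about 0.0001 QALY;
- high end: 0.05 × 28/365 × 0.30 = 0.00115, about 0.0012 QALY.

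**Step 4: does another part of the plan absorb it?** Section 8.2 has a sensitivity analysis with a healthy cohort from a separate study as baseline. The rater in that cohort is not stated, so it cannot be relied on to restore a same-rater comparison.

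**The case against.** **The text leaves other readings open.** Section 6.4.3 speaks of children's own questionnaires without limiting them to diaries. The document list in section 3 names no enrolment form for parent or child, so the absence of a child version there shows little. This stands as a caution. Even so, section 6.4.3 names the parent as the scorer of the baseline, and the sentence about self-completion follows the description of the diary.

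**Both diary versions may run in parallel.** If so, choosing between them is a rule that an analysis plan could supply. That is fair, but nothing in the protocol says the proxy diary continues once the child self-completes, and a rule written later cannot recover scores that were not collected.

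**Stronger readings that the documents do not support:**

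- *Older children are mostly self-rated, so a planned age comparison is confounded with rater.* Self-completion is an option, and its uptake is unknown. Section 8.1.1 speaks of quantifying differences for different ages and names subgroup analysis only for complication type. No age bands or test between ages are given, so a false-positive rate for such a test would have no basis here.
- *The rater changes systematically with illness, with the parent rating the worst days.* This is possible, but nothing in the protocol says so.
- *The offset can equal the true loss.* The benchmarks in section 4.1.2 (Impact on Health Related Quality of Life), 4 and 10 QALYs per 1000, come from children not selected as hospital cases. The protocol itself says the loss in hospitalised UK children has not been assessed.
- *The offset accumulates over six months.* Arithmetically, 0.02 to 0.05 over 182 days is 0.010 to 0.025 QALY. However, the window in section 8.2 closes when the parents judge health normal, so this applies only to a child whose loss lasts that long.

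The carer part of the primary outcome is not affected.

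**Conclusion.** The point holds in a limited form. For children over 7 who choose to self-complete, the protocol provides only a parent-scored baseline, allows child-scored follow-up, and has no rule that the rater must match. The illustrative shift is 0.0015 to 0.0038 QALY per self-reporting child at 28 days. For the cohort mean it is about 0.0001 to 0.0012 QALY, which is probably small. These figures rest on an assumed offset of 0.02 to 0.05, an assumed duration and an assumed 5% to 30% self-rating. The direction is unknown. What is at stake is mainly the estimates for older children, whose age-specific results would partly reflect who completed the form. It is worth correcting because the remedy is cheap and the missing score cannot be supplied by analysis afterwards.

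**What to change.** **Section 6.4.3.** Have each child who will self-complete also give a recalled pre-illness score at enrolment, together with the consent-day or worst-day score. Record the rater on every entry.

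**Section 8.2.** State that each child's QALY loss uses the same rater at baseline and follow-up. Where the rater switches, use the parent-proxy series if it was collected. Add a proxy-only analysis across all ages as a sensitivity analysis for by-age results. Making proxy report primary at every age is not required: it would set aside self-report from children the protocol considers able to give it.

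**Cost.** One short extra child questionnaire at enrolment, a rater tick-box and a few sentences of protocol text. If the proxy series is kept running alongside self-report, parents of self-completing children also have some extra entries; section 6.4.3 puts the whole diary at under five minutes.

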6.5. Definition of End of Study

The study is planned to recruit for up to 12 months and end of study will be the date of last diary entry of the last participant (up to 6 months after the last participant discharged from hospital).

7. DETAILS OF SAFETY REPORTING PROCESSES

As a prospective cohort study with no active interventions it will not result in adverse events. Parents should follow normal NHS clinical routes if they become unwell but will have contact details for the PI in case of study specific queries. The study is sponsored by the University of Bristol. The University has Public Liability insurance to cover the liability of the University to research participants.

http://www.bristol.ac.uk/media-

library/sites/secretary/documents/insurance/employersandpublicliabilityletter.pdf.pdf

8. ANALYSIS AND STATISTICAL CONSIDERATIONS

8.1. Methods & Sample size calculation

8.1.1. Primary objectives

We aim to recruit at least 100 families of children with chickenpox in hospital into the HRQoL surveillance arm but would ideally like to recruit 200. This will allow us to adequately quantify the differences in quality of life between ill and healthy states for different secondary complications and different ages. The previous historical recall studies[9],[10] do not describe the distribution of their HRQoL in enough detail to use in a power calculation.[24] Using the EQ5D reference healthy data[25] would suggest a sample size of 100 children would give 90% power to detect a 6% difference in quality of life (p=0.05). However as we would like to perform subgroup analysis for different types of secondary complication this will depend on the number in each group — with a minimum of 25. (personal communication [name] Public Health England), ideally a sample size of 200 will increase the likelihood of capturing enough of each complication type to be able to analyse them separately.

8.1.2. Secondary objectives

These are descriptive analyses so have no formal power calculation. Incidence of complications will be calculated using the paediatric population for the hospital's referral area as a denominator taken from the Office for National Statistics population census.

QoL-PoX-H (IRAS 240389)

8.2. Methods

Quality adjusted life year loss for children and their parents will be calculated as the reduction in HRQoL from baseline (as reported retrospectively prior to illness) for the time period between development of clinical signs and return to what the parents assess is normal health for their child. A sensitivity analysis will be carried out using baseline "healthy" cohort being assessed in a separate study.

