6.2. Primary and Secondary Outcome Measures

6.2.1. Primary outcome measures

The primary outcome of the study is to calculate the loss of Quality Adjusted Life Years (QALYs) and financial cost attributable in the families of children with acute VZV infection. This will be measured by standard quality of life tools (EQ5D-5L[21] and CHU9[22] in children) and EQ5D-5L in adults.

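### The protocol computes carer QALY loss from a recalled pre-illness baseline, but its description of data collection obtains that baseline for the child only

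*Protocol*

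**What the plan says.** Carers belong to the primary outcome. The Synopsis gives it as "QALY loss of patients and carers". Section 6.2.1 speaks of families and names the instrument, "EQ5D-5L in adults". Section 4.1.2 (Impact on Health Related Quality of Life) presents the carer measurement as something other studies often leave out: "In our study we will also be assessing carer HRQoL".

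Section 8.2 sets the calculation: "Quality adjusted life year loss for children and their parents will be calculated as the reduction in HRQoL from baseline". The baseline is defined in the same sentence: "as reported retrospectively prior to illness". The period runs from the first clinical signs until the parents judge the child to be back to normal. A healthy cohort from a separate study is to supply the baseline in a sensitivity analysis.

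Section 6.4.3 describes collection. At consent the parent is asked to "score their child's HRQoL at the time of consent", to "retrospectively score their child's HRQoL prior to becoming" ill, and to score the child's worst day if recovery has begun. The parents' own scores come in later: "The diary will consist of illness severity questions and HRQoL questionnaires for the child and their parents". The diary is kept daily or on alternate days in hospital, weekly for a month after discharge, then monthly until symptoms resolve, with a last contact at six months.

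**The concern.** The formula in 8.2 needs two things for each carer: scores during the illness and a score for usual health before it. Section 6.4.3 provides the first and does not mention the second.

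The first diary score cannot supply it. Under section 6.3.2 a family enters only when the child has chickenpox or had it within 21 days (12 months for stroke), so every parental diary score is taken after the illness began. If the parent is already affected by then, that score is not usual health.

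An unseen analysis plan cannot settle this alone. It could name a different carer baseline, but it cannot create a recalled score that was never asked for. At stake is one of the two groups named in the primary outcome. The child's QALY loss, whose baseline is clearly described, is not affected.

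**Working it through.** **Step 1: what 8.2 needs against what 6.4.3 describes.**

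| Score | Child | Carer |
|---|---|---|
| Before illness, recalled at consent | described in 6.4.3 | not described |
| At consent, in the questionnaire | described in 6.4.3 | not described |
| Worst day, if already recovering | described in 6.4.3 | not described |
| Diary in hospital and after discharge | described in 6.4.3 | described in 6.4.3 |
| Healthy cohort | 8.2, sensitivity analysis only | 8.2, sensitivity analysis only; whether it includes adults is not stated |

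No other section describes a pre-illness carer score.

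**Step 2: how a baseline error carries into the result.** Let B be the carer's true pre-illness utility, U(t) the utility on day t, and T the length of the period in days.

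Loss = sum over days of [B − U(t)] / 365.25

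If B is replaced by B + e, every daily term changes by e, so

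Shift in loss = e × T / 365.25

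The shift does not depend on how ill the carer felt. A baseline set too low understates the loss, and one set too high overstates it.

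**Step 3: numbers.** The protocol gives no value for e or T for carers, so both are assumptions: e = 0.02, 0.05, 0.10 and T = 14, 30 days. Results are QALYs per 1000 carers.

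| Error e | 14 days | 30 days |
|---|---|---|
| 0.02 | 0.02 × 14 / 365.25 × 1000 = 0.8 | 0.02 × 30 / 365.25 × 1000 = 1.6 |
| 0.05 | 0.05 × 14 / 365.25 × 1000 = 1.9 | 0.05 × 30 / 365.25 × 1000 = 4.1 |
| 0.10 | 0.10 × 14 / 365.25 × 1000 = 3.8 | 0.10 × 30 / 365.25 × 1000 = 8.2 |

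**Step 4: scale.** The only QALY losses in the protocol are the 4 and 10 per 1000 in section 4.1.2 (Impact on Health Related Quality of Life). They come from recall studies of children, not carers, and the section says that loss in hospitalised UK patients has not been assessed. They show only that errors of this size are not negligible on the scale in use.

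The protocol has no figure of its own for carer loss to reproduce. Its one computed figure, the 90% power in section 8.1.1, concerns 100 children and has no bearing here.

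**The case against.** **The form is not shown.** Section 6.4.3 summarises a brief questionnaire and does not claim to list every item. Section 8.2 plainly intends a recalled baseline for parents, so 6.4.3 may simply be an incomplete description. This stands. A reader might infer that no pre-illness carer score is taken; the document supports only that none is described. One of the two still needs correcting: 6.4.3 if the item exists, the form if it does not.

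**Carer loss can still be estimated.** Late diaries, or the six-month contact, may give a carer score after recovery. This also stands, so a reader who concludes that carer loss cannot be estimated at all goes too far. But 8.2 does not name such a score as the baseline. Section 6.5 implies a diary entry as late as six months after discharge, yet the protocol does not say outright that the parent's EQ5D-5L is completed then.

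**The size could be exaggerated.** One could take the first diary as baseline, assume a constant deficit, and show that almost all the carer loss disappears. The protocol never proposes that baseline, and the near-zero answer would follow from the assumption. It is not evidence of what this study would report.

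**The weight of carers in the primary outcome.** Carers are one of two named groups, but the protocol gives no weights. Calling them half of the primary outcome would have no support.

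**Conclusion.** The point holds as a mismatch between two sections. Section 8.2 requires a recalled pre-illness score for each carer, and 6.4.3, the only account of how that score is collected, provides it for the child only. Followed as written, the protocol does not yield carer QALY loss by its own stated method. Approximation from post-recovery scores remains possible.

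The textual finding rests on no numerical assumption. It is conditional on the unseen enrolment form: if the form already asks the question, the fault lies in the description and not in the data. The size, about 0.8 to 3.8 per 1000 over 14 days and 1.6 to 8.2 per 1000 over 30 days, depends on assumed baseline errors of 0.02 to 0.10 and assumed durations. It is a range of sensitivity, not an estimate of the bias that will occur.

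**What to change.** 1. Check the enrolment form. If it already has a pre-illness item for the carer, one sentence in 6.4.3 is enough.
2. If it does not, add two EQ5D-5L forms for each participating carer at enrolment, one recalled for the time before the child became ill and one for the day of consent. Amend 6.4.3 to say so.
3. For families already enrolled without the item, state in 8.2 that the carer's own post-recovery score serves as baseline. This would be a late diary, or the six-month contact if the parent's EQ5D-5L is completed then. Flag these families in the analysis. Where the child still has sequelae, the carer may not be back to usual health, and a late score may then understate the loss.
4. Keep the healthy cohort as the sensitivity analysis, and say whether it includes adults.

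The cost is a short amendment and slight extra burden on parents at consent. The recalled carer score has the same recall limits that the protocol already accepts for the child.
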